9.3.1 Packaging and Labeling

Before the shipment to the investigative sites, Investigational Product and Placebo will be labeled with the protocol number, contents ("ALD403" or "Placebo"), directions for storage, the Sponsor, and any other information required by regulatory agencies, such as a statement that it is limited to investigational use. Investigational Product and Placebo to be administered to the subject will be labeled by the investigators in a manner (after dose preparation) that protects blinding.

9.3.2 Blinding

This clinical trial is double-blind, meaning the subjects and site personnel are blinded to treatment assignment, except for clinical trial site's unblinded pharmacist or Investigational Product consignee. The study site must have a written plan in place to ensure blinding is adequately maintained for the study. If the blind is broken, the date, time and reason must be recorded. The blind should only be broken for reasons in which knowledge of the Investigational Product is critical to the subject safety and /or trial management. The Principal Investigator will report any cases of unblinding to the sponsor within 24 hours of the incident.

Immediately prior to PK/immunogenicity sample analysis, the bioanalytical laboratory will be unblinded in order to obtain the treatment assignments. The study will remain blinded until the

last subject has completed the Week 24 visit at which time aggregate efficacy and safety data will be unblinded.

9.3.3 Storage and Handling of Investigational Product

Investigational Product/Placebo will be stored at a central depot or at the clinical site at -20°C (-10°C to -25°C) in accordance with any accompanying instructions. Please refer to the Pharmacy Manual for additional storage and handling procedures. Diluent (0.9% saline) will be stored according to institutional standards.

Investigators shall take adequate precautions, including storage of the Investigational Product and Placebo in a securely locked, substantially constructed cabinet or other securely locked, substantially constructed enclosure, access to which is limited to maintain blind, prevent theft or diversion of the substance into illegal channels of distribution.

9.3.4 Accountability and Disposition of Investigational Product

The Investigator is responsible for maintaining accurate Investigational Product and Placebo accountability records throughout the clinical trial. The site must maintain a record of Investigational Product Accountability Log on which the unblinded responsible pharmacist, or designee, will record the receipt, lot number/retest date, quantity, dispensation and return of Investigational Product to the Pharmacy, as well as any destruction of Investigational Product/Placebo including empty Investigational Product/Placebo containers (e.g., vials) or returns to the Sponsor. Where more than one secure area is being used for storage at a site, all movement of Investigational Product through the Chain of Custody must be recorded in accountability records such that full reconciliation may be completed at the end of the trial.

Included with each Investigational Product or Placebo shipment is a form listing lot numbers and quantity shipped. The Investigator, responsible pharmacist, or designee, will sign and return to Alder BioPharmaceuticals, Inc., or designee, a statement that certifies the receipt and integrity of these supplies. A copy will be retained for the site clinical trial file.

After completion of the clinical trial, the Investigator is responsible for either returning or destroying (if authorized by Sponsor) all unused Investigational Product/Placebo. The Investigator must verify that no remaining supplies are in his/her possession. All used/partially used vials/IV bags will be destroyed onsite according to the site SOPs. Where the Sponsor has

indicated in writing that Investigational Product/Placebo is to be destroyed on site, destruction must be in accordance with local regulations for the product type and destruction documentation must be provided to the Sponsor.

If the clinical trial is terminated, suspended, discontinued, or completed, the Investigator or designee shall return the unused supplies to the Sponsor or designee, or otherwise provide for disposition of the unused supplies (as authorized by the Sponsor).

9.4 Concomitant Medications

Any concomitant therapy, used from the time the subject signs the informed consent through Week 56, must be recorded on the CRF, including medications required for treatment of any AEs or SAEs. The Medical Monitor or designee should be notified in advance of (or as soon as possible after) any instances in which restricted therapies are administered. Use of regular prescription medications for condition other than migraine must be preapproved by Medical Monitor.

The following medications are **restricted** through Week 24:

- Any prophylactic headache medication (any preventive medication or supplement with evidence of efficacy from at least 1 placebo-controlled trial, see Section 15.1) is prohibited.
- Barbiturates and prescription opiates are allowed for ≤ 4 days per month through Week
 24, provided the subject does not meet the criteria for Medication Overuse Headache and has been on a stable regimen (≤ 4 days per month) for at least 2 months prior to screening. Drugs containing non-prescription codeine (16 mg or less) are permitted.
- Botulinum toxin for migraine or for any other medical/cosmetic reasons requiring injections in the head, face, or neck are prohibited 4 months prior to screening through Week 24.
- Devices, neuromodulation, neurostimulation, or injectable therapy (trigger point injections, extracranial nerve blocks, facet joint injections) for headache prophylaxis are prohibited 2 months prior to screening through Week 24.

10 Schedule of Assessment and Procedures

Assessment and procedures at each visit are summarized in Section 2 (Schedule of Events and Assessments). An electronic headache eDiary will be distributed to each subject at the time of screening visit. The subject will record information daily regarding headache characteristics, severity and length. Compliance data from the eDiary will be made available and reviewed by the trial site.

10.1 Screening Day (Day -35 to -29)

The following assessments will be performed and measurements recorded:

- Written informed consent
- Inclusion/exclusion criteria reviewed
- Demographics (gender, age, race, ethnicity)
- Medical history including Migraine History
- Height and body weight
- Physical examination
- Vital signs including blood pressure (BP) and pulse
- Beck Depression Inventory (BDI-II)
- Columbia-Suicide Severity Rating Scale (C-SSRS) Baseline/Screening Version
- 12-lead ECG
- Clinical laboratory tests, including hematology, serum chemistry, and serology (including HIV, Hepatitis B and Hepatitis C)
- Urine drugs of abuse screening
- Pregnancy test (urinary hCG) on all female subjects
- Adverse events
- Concomitant medications
- Distribute headache eDiary and instruct subject on completion and compliance of diary

10.2 Day 0 (Randomization and Treatment)

Day 0 must be 29 to 35 days after the screening visit.

The following assessments will be performed pre-dose (unless otherwise specified) and measurements recorded with review of data from eDiary:

- Review inclusion/exclusion criteria including:
 - o Verification of completion of eDiary for at least 25 of 28 days following screening
 - Verification that during the 28 day period following screening, the subject experienced ≤ 14 headache days of which at least 4 have to be migraine days (migraine days count as headache days) as recorded in the eDiary.
- Body weight
- Physical examination
- Brush allodynia test
- Vital signs including BP and pulse
 - Vital signs will be obtained and recorded prior to the start of Investigational Product infusion and 4 hours post-end of infusion (± 30 minutes).
- C-SSRS Since Last Visit Version
- 12-lead ECG
 - 12-lead ECGs will be performed prior to the start of Investigational Product infusion and 4 hours post-end of infusion (± 30 minutes)
- Clinical laboratory tests, including hematology and serum chemistry
- Pregnancy test (urinary hCG) on all female subjects
 - Subjects with a positive pregnancy test will not be dosed and will be withdrawn from the trial
- Plasma Free ALD403 PK sample
 - Blood will be drawn pre-dose (within one hour prior to Investigational Product administration)
- A blood sample will be taken pre-dose for baseline determination of anti-ALD403 antibodies in serum (immunogenicity)
- SF-36 v2.0, EQ-5D-5L and ASC-12 completion by subject
- Adverse events (throughout visit)
- Concomitant medications (throughout visit)
- Randomize subject via the IWRS or IVRS system

 Dosing of ALD403 or Placebo; subject must be monitored for at least 4 hours after the dosing completion

10.3 Week 4 Visit (Day 28 ± 3 days)

The following assessments will be performed and measurements recorded:

- Headache eDiary data reviewed by trial site
 - Review compliance with completion of eDiary; if subject is not compliant with the daily eDiary, instruct regarding importance of daily completion
- Brush allodynia test
- Vital signs including BP and pulse
- C-SSRS Since Last Visit Version
- 12-lead ECG
- Clinical laboratory tests, including hematology and serum chemistry
- Plasma Free ALD403 PK sample
- A blood sample will be taken for anti-ALD403 antibodies in serum (immunogenicity)
- SF-36 v2.0, EQ-5D-5L and ASC-12 completion by subject
- Adverse events
- Concomitant medications

10.4 Week 8 Visit (Day 56 ± 3 days)

The following assessments will be performed and measurements recorded:

- Headache eDiary data reviewed by trial site
 - Review compliance with completion of eDiary; if subject is not compliant with the daily eDiary, instruct regarding importance of daily completion
- Vital signs including BP and pulse
- C-SSRS Since Last Visit Version
- 12-lead ECG
- Plasma Free ALD403 PK sample
- A blood sample will be taken for determination of anti-ALD403 antibodies in serum (immunogenicity)

- SF-36 v2.0, EQ-5D-5L and ASC-12 completion by subject
- Adverse events
- Concomitant medications

10.5 Week 12 Visit (Day 84 ± 3 days)

The following assessments will be performed pre-dose (unless otherwise specified) and measurements recorded:

- Headache eDiary data reviewed by trial site
 - Review compliance with completion of eDiary; if subject is not compliant with the daily eDiary, instruct regarding importance of daily completion
- Brush Allodynia test
- Vital signs including BP and pulse
 - Vital signs will be obtained and recorded prior to the start of Investigational Product infusion and 4 hours post-end of infusion (± 30 minutes).
- C-SSRS Since Last Visit Version
- 12-lead ECG
 - 12-lead ECGs will be performed prior to the start of Investigational Product infusion and 4 hours post-end of infusion (± 30 minutes)
- Clinical laboratory tests, including hematology and serum chemistry
- Pregnancy test (urinary hCG) on all female subjects
- Plasma Free ALD403 PK sample
 - Blood will be drawn pre-dose (within one hour prior to Investigational Product administration)
- A blood sample will be taken pre-dose for baseline determination of anti-ALD403 antibodies in serum (immunogenicity)
- SF-36 v2.0, EQ-5D-5L and ASC-12 completion by subject
- Adverse events
- Concomitant medications
- Dosing of ALD403 or Placebo; subject must be monitored for at least 4 hours after the dosing completion

10.6 Week 16 Visit (Day 112 ± 3 days)

The following assessments will be performed and measurements recorded:

- Headache eDiary data reviewed by trial site
 - Review compliance with completion of eDiary; if subject is not compliant with the daily eDiary, instruct regarding importance of daily completion
- Brush allodynia test
- Vital signs including BP and pulse
- C-SSRS Since Last Visit Version
- Plasma Free ALD403 PK sample
- A blood sample will be taken for determination of anti-ALD403 antibodies in serum (immunogenicity)
- SF-36 v2.0, EQ-5D-5L and ASC-12 completion by subject
- Adverse events
- Concomitant medication

10.7 Week 20 Visit (Day 140 ± 3 days)

The following assessments will be performed and measurements recorded:

- Headache eDiary data reviewed by trial site
 - Review compliance with completion of eDiary; if subject is not compliant with the daily eDiary, instruct regarding importance of daily completion
- Brush allodynia test
- Vital signs including BP and pulse
- C-SSRS Since Last Visit Version
- Plasma Free ALD403 PK sample
- A blood sample will be taken for determination of anti-ALD403 antibodies in serum (immunogenicity)
- SF-36 v2.0, EQ-5D-5L and ASC-12 completion by subject
- Adverse events
- Concomitant medications

10.8 Week 24 Visit (Day 168 +3 days)

Week 24 must be done on the target day or 3 days after. Three days earlier than target date is not allowed. The following assessments will be performed and measurements recorded:

- Headache eDiary data reviewed by trial site
 - Review compliance with completion of eDiary; if subject is not compliant with the daily eDiary, instruct regarding importance of daily completion
- Body weight
- Physical examination
- Brush allodynia test
- Vital signs including BP and pulse
 - Vital signs will be obtained and recorded prior to the start of Investigational Product infusion and 4 hours post-end of infusion (± 30 minutes).
- C-SSRS Since Last Visit Version
- 12-lead ECG
 - 12-lead ECGs will be performed prior to the start of Investigational Product infusion and 4 hours post-end of infusion (± 30 minutes)
- Clinical laboratory tests, including hematology and serum chemistry
- Pregnancy test (urinary hCG) on all female subjects
- Plasma Free ALD403 PK sample
 - Blood will be drawn pre-dose (within one hour prior to Investigational Product administration)
- A blood sample will be taken pre-dose for baseline determination of anti-ALD403 antibodies in serum (immunogenicity)
- SF-36 v2.0, EQ-5D-5L and ASC-12 completion by subject
- Adverse events
- Concomitant medications
- Dosing of ALD403 or Placebo; subject must be monitored for at least 4 hours after the dosing completion

10.9 Week 28 Visit (Day $196 \pm 7 \text{ days}$)

The following assessments will be performed and measurements recorded:

- Headache eDiary data reviewed by trial site
 - Review compliance with completion of eDiary; if subject is not compliant with the daily eDiary, instruct regarding importance of daily completion
- Vital signs including BP, pulse
- 12-lead ECG
- Clinical laboratory tests, including hematology and serum chemistry
- C-SSRS Since Last Visit Version
- Adverse events
- Concomitant medications

10.10 Week 36 Visit (Day 252 \pm 3 days)

The following assessments will be performed pre-dose (unless otherwise specified) and measurements recorded:

- Headache eDiary data reviewed by trial site
 - Review compliance with completion of eDiary; if subject is not compliant with the daily eDiary, instruct regarding importance of daily completion
- Physical examination
- Body weight
- Vital signs including BP, pulse will be obtained prior to the start of Investigational Product infusion and 4 hours post-end of infusion (± 30 minutes)
- 12-lead ECG
 - 12-lead ECGs will be performed prior to the start of Investigational Product infusion and 4 hours post-end of infusion (± 30 minutes)
- Clinical laboratory tests, including hematology and serum chemistry
- Pregnancy test (urinary hCG) on all female subjects
- C-SSRS Since Last Visit Version
- SF-36

- Plasma Free ALD403 PK sample
 - Blood will be drawn pre-dose (within one hour prior to Investigational Product administration)
- A blood sample will be taken pre-dose for determination of anti-ALD403 antibodies in serum (immunogenicity)
- Adverse events
- Concomitant medications
- Dosing of ALD403 or Placebo; subject must be monitored for at least 4 hours after the dosing completion

10.11 Week 48 Visit (Day 336 + 7 days)

The following assessments will be performed and measurements recorded:

- Return of Headache eDiary
- Vital signs including BP, pulse
- 12-lead ECG
- Clinical laboratory tests, including hematology and serum chemistry
- Pregnancy test (urinary hCG) on all female subjects
- Plasma Free ALD403 PK sample
- A blood sample will be taken for determination of anti-ALD403 antibodies in serum (immunogenicity)
- C-SSRS Since Last Visit Version
- Adverse events
- Concomitant medications

10.12 Week 56 Visit (Day 392 ± 7 days) End of Study or Early Termination

The following assessments will be performed and measurements recorded:

- Body weight
- Physical examination
- Vital signs including BP, pulse
- 12-lead ECG

- Clinical laboratory tests, including hematology and serum chemistry
- Pregnancy test (urinary hCG) on all female subjects
- Plasma Free ALD403 PK sample
- A blood sample will be taken for determination of anti-ALD403 antibodies in serum (immunogenicity)
 - Subjects who test positive for anti-ALD403 antibodies at the last study visit will be asked to provide up to 2 additional blood samples for immunogenicity testing at approximately 3 month intervals for up to 6 months.
- C-SSRS Since Last Visit Version
- SF-36
- Adverse events
- Concomitant medications

10.13 Early Termination

All subjects will be encouraged to complete all evaluations through Week 56. However, subjects who prematurely discontinue the study will have Early Termination assessments completed at the time of discontinuation. Subjects who are randomized but do not receive study treatment may discontinue the study without any further procedures.

11 Assessment of Safety

11.1 Adverse Events

11.1.1 Definitions

An adverse event (AE) is any untoward medical occurrence in a patient or clinical investigation participant administered a pharmaceutical product that does not necessarily have a causal relationship with the treatment. An AE can therefore be any unfavorable and unintended sign (including an abnormal laboratory finding), symptom, or disease temporally associated with the use of a medicinal (investigational) product, whether or not related to the medicinal (investigational) product. (ICH E6)

11.1.2 Assessment of Adverse Events

The Investigator is required to monitor the occurrence of adverse events for each subject from the time of informed consent through the course of the clinical trial. Adverse events may be reported by the subject, reported by a caregiver, or reported by the investigative site through Investigator site personnel open-ended questioning, through physical examination, laboratory test, documentation in medical records, or by other means. Adverse events include:

- Any new undesirable medical experience or an unfavorable and unintended change of an
 existing condition that occurs during or after treatment, whether or not considered related
 to the Investigational Product.
- Asymptomatic abnormal findings considered by the Investigator to be clinically significant. For example, abnormal ECG or abnormal lab findings.

A new or worsening of a pre-existing or chronic condition is considered an adverse event and must be reported as such. Medical conditions, which existed prior to the time of informed consent into the clinical trial, will not be considered an adverse event unless the condition worsens. Unchanged, chronic, non-worsening or pre-existing conditions from the time of informed consent are not adverse events and should not be recorded on the AE eCRF.

Pre-existing medical conditions of clinical significance must be included in the subject's medical history and recorded on the medical history eCRF page.

Each event recorded on the AE eCRF is required to be assessed by the Investigator with regard to the following; seriousness, severity, and relationship to Investigational Product, as outlined below.

Seriousness

An adverse event or suspected adverse event is considered serious if in the view of either the Investigator or Sponsor, it results in;

- Death
- Is life-threatening (this means that the subject is at risk of death at the time of the event; it does not mean that the event hypothetically might have caused death if it were more severe)

- Inpatient hospitalization or prolonged existing hospitalization
- A persistent or significant incapacity or substantial disruption of the ability to conduct normal life functions.
- Congenital anomaly/ birth defect
- Important medical events that may not result in death, be life-threatening or require hospitalization may be considered serious when, based upon appropriate medical judgement, they may jeopardize the patient or subject and/or may require medical or surgical intervention to prevent one of the outcomes listed in the definition. (21 CFR 312.32(a) and ICH E2A)

Severity

The severity of an AE will be graded as follows:

- Grade 1 Mild; asymptomatic or mild symptoms; clinical or diagnostic observations only; intervention not indicated.
- Grade 2 Moderate; minimal, local or noninvasive intervention indicated;
 limiting age-appropriate instrumental Activities of Daily Living (ADL).
- Grade 3 Severe or medically significant but not immediately life-threatening; hospitalization or prolongation of hospitalization indicated; disabling; limiting self-care ADL.
- o Grade 4 Life-threatening consequences; urgent intervention indicated.
- Grade 5 Death related to AE.

Relationship to Investigational Product

The Investigator is required to assess the causality/relationship between each AE and the Investigational Product as not related or related and record the assessment on the source documents and in the eCRF AE page. Medical judgment should be used to determine the likely relationship of the AE to the Investigational Product considering all relevant factors including (but not limited to) relevant history, concomitant medical condition and concomitant medications. Determination should be based on assessment of temporal relationships, biologic

plausibility, association (or lack of association) with underlying disease, and presence (or absence) of a more likely cause.

Not Related: It is plausible that the AE has an etiology other than the Investigational Product (e.g., pre-existing condition, underlying disease, concomitant medical condition, or concomitant medication).

Related: The AE cannot reasonably be explained by the subject's clinical state, concomitant\medical condition or concomitant therapies, and a temporal relationship exists between the event onset and administration of the Investigational Product.

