11.1.3 Recording Adverse Events

Event reporting will extend from time of informed consent until completion of the final visit. Serious adverse events occurring after the end of the clinical trial must be reported if the Investigator considers there to be a causal relationship with the Investigational Product.

SAE Notification Form should be used to report any related SAEs which occur after the end of the clinical trial.

Adverse events (AEs) should be recorded on the AE eCRF, whether believed by the Investigator to be related or not related to the Investigational Product.

AE reporting should contain;

- a brief description of the event,
- date of onset,
- date of resolution,
- severity,
- actions taken or treatment required,
- relationship to Investigational Product,
- outcome, and
- whether the event is considered serious.

Whenever possible, the Investigator should group signs or symptoms that constitute a single diagnosis into a single event term. For example, "cough, rhinitis, and sneezing" might be grouped together as "upper respiratory tract infection".

Asymptomatic abnormal findings considered by the Investigator to be clinically significant should be recorded as an AE, unless it is associated with a clinical syndrome that has already been reported as an AE.

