11.1.5 Unexpected and Related Serious Adverse Events

Unexpected SAEs are those which:

- Are not previously reported as associated with ALD403, as referenced in the Investigator's Brochure.
- May be symptomatically and pathophysiologically related to an AE listed in the Investigator's Brochure, but differ from the event due to greater severity, frequency or specificity.

The Sponsor or designee will report, to the appropriate regulatory authorities according to local and regulatory requirements, unexpected SAEs which are considered related to ALD403 (suspected unexpected serious adverse reactions [SUSARs]). The clinical trial site personnel are responsible for reporting these events to their EC/IRB in accordance with applicable local and regulatory requirements.

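### The Related / Not Related definitions in Protocol 11.1.2 conflict with the assessment factors just before them, and applied as written they move events in one direction, out of Related

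*Protocol*

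**What the plan says.** Protocol 11.1.2, under the relationship heading, sets a two-category scale. The investigator must assess the "causality/relationship between each AE and the Investigational Product as not related or related".

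The instruction on method comes first: "Medical judgment should be used to determine the likely relationship of the AE to the Investigational Product considering all relevant factors". Four factors are then listed: timing, biologic plausibility, association with underlying disease, and "presence (or absence) of a more likely cause".

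Two definitions follow:

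- **Not Related:** "It is plausible that the AE has an etiology other than the Investigational Product". The examples given in brackets include underlying disease and concomitant medication.
- **Related:** "The AE cannot reasonably be explained by the subject's clinical state", concomitant conditions or concomitant therapies, and in addition "a temporal relationship exists between the event onset and administration of the Investigational Product".

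The classification is used in three main places:

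- **Treatment-related tables.** Protocol 13.4.4.1 and SAP 3.6.1 tabulate treatment-related events beside all events. The SAP gives no causality definition of its own.
- **SAEs after the trial ends.** Under Protocol 11.1.3 these "must be reported if the Investigator considers there to be a causal relationship with the Investigational Product".
- **SUSARs.** Protocol 11.1.5 defines them as "unexpected SAEs which are considered related to ALD403", without saying in whose judgment.

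**The concern.** The factors ask a comparative question: is the product or something else the likelier cause? The definitions ask an absolute one: is any other cause plausible? With no intermediate category, an event for which both the product and another cause are credible has to go to one side, and the definitions send it to Not Related even when the product is the likelier explanation.

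This matters because the field is required for every recorded AE. A rule that can only remove events from the related category makes the treatment-related tables read low. It also narrows the only route that the protocol describes for SAEs after the trial ends. Protocol 5.4 itself says that long-term data are limited, so a late related SAE is an event that the sponsor would want to hear about.

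**Working it through.** The documents give no expected number of related AEs or SUSARs, so there is no planned figure to reproduce. The check compares the two rules case by case and then traces where the classification is used.

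**Step 1. Compare the rules, given that the timing fits.**

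| Case | Weighing which cause is likelier | Definitions as written | Agree? |
|---|---|---|---|
| (a) Product likelier, no other plausible cause | Related | Related | Yes |
| (b) Product likelier, another cause plausible | Related | Not Related | **No** |
| (c) Another cause likelier | Not Related | Not Related | Yes |

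Only case (b) conflicts. There the definitions move the event from Related to Not Related, and no case moves the other way. The error therefore has one direction.

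**Step 2. Trace the consequences.**

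- *Treatment-related AE/TEAE tables:* affected directly, because they use the investigator's field.
- *SAEs after the trial ends:* affected directly. A case (b) event meets the definition of Not Related, so Protocol 11.1.3 does not require a report.
- *On-study SAEs:* site reporting is unaffected. Protocol 11.1.4 requires it within 24 hours whatever the causality call.
- *SUSARs:* uncertain. Protocol 11.1.4 leaves the decision on expedited reporting to the sponsor or its designee, and 11.1.5 does not name the assessor. The documents offer no causality definition other than the one in 11.1.2.
- *All AEs and TEAEs:* unaffected, because they are tabulated regardless of causality.

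**Step 3. Illustrate the size (an assumption, not in the documents).** Let q be the share of events that weighing would call Related but that also have a plausible alternative. The share that remains Related is 1 − q:

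- q = 10%: 90% remain
- q = 30%: 70% remain
- q = 50%: 50% remain

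If q is the same in an ALD403 arm (related-event rate r_A) and the placebo arm (rate r_P), the ratio is unchanged: r_A(1 − q) / [r_P(1 − q)] = r_A / r_P. The difference shrinks to (1 − q)(r_A − r_P). If q differs between arms, the ratio changes too, by the factor (1 − q_A)/(1 − q_P).

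These are event counts. The planned tables count subjects, and a subject leaves a row only if every such event is reclassified, so the change in subject incidence need not equal q.

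**The case against.** The case on the other side has five parts.

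1. **The comparative question is one factor of four, not a stand-alone test, and nothing ranks the definitions above the instruction to use judgment.** This is right, and it confines the conflict to case (b). It does not remove it. If some investigators follow the factors and others the definitions, the related counts mix two thresholds.

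2. **SUSARs.** A reader might infer that SUSAR counts are suppressed. The documents do not support that as fact. On-study SAEs reach the sponsor whatever the causality call, the medical monitor or designee reviews them and may go back to the investigator, and the sponsor decides on expedited reporting. Only the post-trial route depends expressly on the investigator.

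3. **Size.** A reader might infer that the related count could fall almost to zero, because the common events in Protocol 5.4 (infections, back pain, dizziness, headache) often have another possible cause. That list pools subjects on ALD403 and placebo and carries no causality data. It cannot support an estimate.

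4. **A gap in the definitions.** An event with no alternative cause and no clear timing may seem to fit neither category. This is weak: the bracketed examples under Not Related are open-ended, and poor timing can itself make another etiology plausible. It is still a reason to make the categories explicitly exhaustive.

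5. **The main safety comparison is intact.** All AEs, severity, SAEs and discontinuations are summarized by arm, assessment is blinded, and a DMC reviews safety data. This stands. It limits the importance of the point but does not answer it for the related tables or for post-trial SAEs.

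**Conclusion.** The conflict is real and can be seen from Protocol 11.1.2 alone. Events for which the product is the likelier cause, but for which another cause is plausible, are classed Not Related under the written definitions.

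The firm consequences are two: treatment-related AE/TEAE counts that are too low, and possible non-reporting of SAEs after the trial ends. An effect on SUSAR classification is possible but not established. The efficacy analyses, the overall AE tables and on-study SAE reporting by sites are untouched.

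The direction is certain to the extent that investigators apply the definitions as written. The size cannot be computed from the documents. That the ratio between arms is preserved rests on the assumption that the reclassified share is equal across arms; blinding makes this reasonable but does not guarantee it.

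**What to change.** - **Protocol 11.1.2:** bring the two definitions and the factor list to one threshold, with categories that do not overlap and that cover every event. For example: Not Related only when another cause is more likely than the product, or when the timing rules out a contribution; Related otherwise. The exact threshold is the sponsor's choice, but every event must meet one definition and only one.
- **Protocol 11.1.5:** state whose causality assessment governs SUSAR classification, the investigator's, the sponsor's or either.

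The cost is a wording amendment and a notice to sites, with somewhat more events classed as related. There is also a cost of timing. A footnote to Protocol Table 5.3 says that enrollment in this trial is complete and subjects are in follow-up. Events already classified must therefore be re-assessed under the new wording, or the treatment-related tables must state that the definition changed and when. Otherwise one table would mix two definitions without saying so.
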